### **6.8 Multiplicity Adjustment**

Secondary endpoints will provide insights regarding the value of this therapy. The most clinically important secondary endpoints are neurologic morbidity and the mRS scores at the 3 to 6 month visit.

To control type I error across these endpoints we will use a step-wise gate keeping procedure for four hierarchical families of hypotheses, tabled below.

Family	Hypothesis	Description
F1	H1	There is no difference in the risk of angiographic occlusion between randomization groups
F2	H2	There is no difference in the risk of neurologic morbidity between randomization groups
F3	H3	There is no difference in the distribution of mRS at the 3 to 6 month visit
F4	H4	There is no difference in the distribution of mRS at the 3 to 6 month visit within patients with an aneurysm status of recently ruptured
	H5	There is no difference in the distribution of mRS at the 3 to 6 month visit within patients with an aneurysm status of not recently ruptured

The type I error control procedure will be as follows:

1. Test the hypothesis in F1
  - a. If the p-value is greater than or equal to 0.05 stop and conclude no treatment effect
  - b. If the p-value is less than 0.05 proceed to step 2
2. Test the hypothesis in F2
  - a. If the p-value is greater than or equal to 0.05 stop and conclude a treatment effect in F1 only
  - b. If the p-value is less than 0.05 proceed to step 3
3. Test the hypothesis in F3
  - a. If the p-value is greater than or equal to 0.05 stop and conclude a treatment effect in F1 and F2 only
  - b. If the p-value is less than 0.05 proceed to step 4
4. Test the hypotheses in F4 using a 0.05-level Holm-step down procedure. With this procedure, the p-values of both tests are ranked from smallest to largest.
  - a. If the smallest p-value is greater than 0.025, stop and conclude a treatment effect in F1, F2, and F3 only
  - b. If the smallest p-value is less than 0.025 and the largest p-value is greater than 0.05, stop and conclude a treatment effect in F1, F2, F3 and H4 or H5 (whichever had the smallest p-value) only
  - c. If the smallest p-value is less than 0.025 and the largest p-value is less than 0.05, declare a treatment effect across F1, F2, F3 and F4

While other secondary endpoint data will be featured in the publication of the trial, there will be no formal correction of the Type I error rate for multiple testing of statistical hypotheses for any of the other secondary endpoints.

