## 3. STUDY OVERVIEW

### 3.1 Study Design

This is a prospective, multi-center, randomized, clinical trial in patients with mid-size aneurysm. Patients will be randomized (1:1) to receive either larger diameter coils or smaller diameter coils.

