## 6. STATISTICAL METHODOLOGY

### 6.1 General Principles

Study day will be calculated from the reference start date and will be used to show the study days of assessments and events. Reference start date is defined as the date of randomization unless otherwise specified.

Continuous variables will be summarized using the following descriptive statistics: number of non-missing values, means, standard deviations, medians, interquartile range, maximum, and minimum. Categorical variables will be summarized using number of non-missing values, counts, and percentages.

Rates of events will be calculated as the ratio of the total number of events recorded divided by the total patient-time. Total patient-time will be calculated by summing the time (in study time units, e.g., days or months) that patients were at risk for a specific event from the reference time point until either study exit or the end of the time period of interest. Rates and their 95% confidence intervals will be reported. Time-to-event variables will be summarized using the Kaplan-Meier method or, in the presence of competing risk, by cumulative incidence curves accounting for competing events as appropriate.

In the situation where an event date is partial or missing, study day, and any corresponding durations are to appear partial or missing in listings. If a partial event date is recorded (i.e. the month and year are known but not the day) and is necessary to calculate patient-time at risk or patient-time to the event, the missing event day will be imputed to the 15th day of the known month and year.

For any variable measured at multiple points in time, change from baseline will be calculated as the difference between the value of the variable at a specific point in time (e.g. 1 year) minus the baseline value. Relative change from baseline will be calculated as the value of a parameter at a specific point in time minus the baseline value of the parameter divided by the baseline value of the parameter. Percent change will be calculated as the relative change multiplied by 100.

All hypothesis testing will be conducted at the 0.05 two-sided significance level unless otherwise specified. P-values will be rounded to three decimal places. P-values less than 0.001 will be reported as <0.001 in tables. P-values greater than 0.999 will be reported as >0.999.

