### 6.5.2 *Determination of Sample Size*

Sample size calculations were based on the primary endpoint under the following assumptions and operating characteristics: a) 73% angiographic occlusion at the 12-18 month visit in patients receiving smaller coils (control arm); b) a 9% absolute improvement (to 82%) in the incidence of angiographic occlusion in patients receiving larger coils; c) Approximately 80% power on a two-sided proportion test; and d) a significance level of 0.05. A sample size of 650 (325 in each arm) will allow us to detect the specified effect size with adequate power. Sample size was calculated using the `power.prop.test` function in R (R Core Team 2021).

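### SAP 6.8 step 1a turns a non-significant primary test into a finding of no effect, which a superiority test without an equivalence margin cannot establish

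*Combined protocol and SAP*

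**What the plan says.** SAP 6.8 sets out a hierarchical procedure with four families of hypotheses. The first family holds the primary null hypothesis: "There is no difference in the risk of angiographic occlusion between randomization groups". Step 1a says what to do if it is not rejected: "If the p-value is greater than or equal to 0.05 stop and conclude no treatment effect".

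The test behind that step is described in SAP 6.5.1. It is a Wald test of a zero treatment coefficient in a log-binomial model, against a two-sided alternative at the 0.05 level. SAP 6.5.1 also plans the risk ratio with its 95% confidence interval, whether or not the test is significant. SAP 6.1 sets the general level: "All hypothesis testing will be conducted at the 0.05 two-sided significance level unless otherwise specified".

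SAP 6.5.2 sizes the trial for a 73% control rate and "a 9% absolute improvement (to 82%) in the incidence of angiographic occlusion in patients receiving larger coils", with "Approximately 80% power on a two-sided proportion test" and 325 patients per arm. Protocol section 9.1 has the same rates, power and sample size. Neither document gives an equivalence or non-inferiority margin, or any other rule for reading a non-significant primary result.

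**The concern.** Failing to reject a hypothesis of no difference is not evidence that there is no difference. To conclude absence of effect, a plan needs a margin below which a difference is regarded as unimportant, and an interval that lies inside it. This plan has no margin, and step 1a looks only at the p-value.

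What is at stake is the sentence the trial may write about its main question. The SAP says that its analyses will go into abstracts and manuscripts. Followed literally, step 1a would have a report state that larger coils have no effect on occlusion beside a confidence interval that still contains the benefit the trial was designed to find.

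**Working it through.** **Inputs.** Control rate 73%, larger-coil rate 82%, 325 per arm, two-sided 0.05 (SAP 6.5.2 and 6.1); 1:1 allocation (SAP 3.1). Complete data are assumed throughout, and differences are in percentage points.

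**1. The plan's own power.** For two proportions with pooled variance under the null:

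z = [Δ√n − 1.96·√(2p̄(1−p̄))] / √(p₁(1−p₁) + p₂(1−p₂))

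With Δ = 0.09, n = 325 and p̄ = 0.775:

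z = (0.09 × 18.028 − 1.96 × 0.5906) / 0.5871 = 0.792, so power = 78.6%.

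This reproduces the stated power of about 80%. The Wald test on the log risk ratio, which is closer to the planned analysis, gives 77.9%.

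**2. How often step 1a is reached.** This is one minus power, from the same formula with control at 73%:

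| True gain (points) | Chance that p ≥ 0.05 |
|---|---|
| 9 (planned) | 21% |
| 8 | 32% |
| 7 | 44% |
| 6 | 57% |
| 5 | 68% |

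Only the first row is the planned benefit. The others are illustrations.

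**3. Which non-significant results leave the design effect open.** With the control arm observed at 73% and an observed gain d, the 95% interval is d ± 1.96·√[0.73×0.27/325 + p₂(1−p₂)/325], where p₂ = 0.73 + d:

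| Observed gain | 95% CI for the difference | Two-sided p | Contains 9 points? |
|---|---|---|---|
| 2.2 | −4.5 to 8.9 | 0.52 | No |
| 2.3 | −4.4 to 9.0 (upper limit 9.03) | 0.50 | Yes, just |
| 4.0 | −2.7 to 10.7 | 0.24 | Yes |
| 6.5 | 0.0 to 13.0 (lower limit −0.02) | 0.051 | Yes |
| 6.6 | 0.1 to 13.1 | 0.047 | Significant |

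Non-significant gains of about 2.3 to 6.5 points are therefore inconclusive about the planned effect. Below about 2.3 points the interval excludes it.

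**4. The same check on the planned scale.** The design effect as a risk ratio is 0.82/0.73 = 1.12. The standard error of the log risk ratio is √[0.27/(325×0.73) + (1−p₂)/(325·p₂)].

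- At an observed gain of 6.5 points this is 0.0439. The risk ratio is 0.795/0.73 = 1.09, with 95% CI 0.999 to 1.19. Step 1a applies, although 1.12 lies well inside the interval.
- The lower edge of the band moves slightly. At 1.9 points the risk ratio is 0.749/0.73 = 1.026, the standard error is 0.0466 and the upper limit is 1.124, just above 0.82/0.73 = 1.123.

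**5. What an equivalence conclusion would need.** The documents give no margin, so one has to be assumed. Take ±9 points, both arms truly at 73%, and two one-sided tests at 0.05 each:

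n = 2 × 0.73 × 0.27 × (1.645 + 1.282)² / 0.09² ≈ 417 per arm for 80% power.

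With one-sided 0.025 each it is 512 per arm. At 325 per arm the power is about 65% and 47% respectively. Even with so wide a margin, the trial is not sized to show equivalence.

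**The case against.** The strongest reply is that step 1a is gatekeeping shorthand. The steps are introduced as a procedure for type I error control, and in the run of outcomes (none, first family only, first two families only) step 1a is simply the empty list. Stopping there is right and familywise error is protected. That part stands. But the SAP nowhere says that the phrase means only that no effect is claimed. The later steps use the same verb for a substantive claim of effect, so the literal reading is the natural one.

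A second reply is that SAP 6.5.1 already plans the risk ratio and its 95% interval. This also stands, and it limits the harm because readers will see the interval. Step 1a does not refer to it, however, so the interval and the prescribed conclusion can disagree.

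A third reply is that the 21% is just one minus the declared power. That is correct. Any trial with this power has it, and the hierarchy would stop in the same trials under any wording.

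A reader might also infer that steps 2a to 4a make the same mistake. They do not: they list the families in which an effect is claimed, and say nothing about absence of effect in the family that failed.

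**Conclusion.** Step 1a is wrong as written, at low severity, and the point is confined to that step. It prescribes a conclusion of no effect that a two-sided superiority test without a margin does not support. It also fails to separate inconclusive results (observed gains of about 2.3 to 6.5 points) from those whose interval excludes the 9-point gain (observed gains below about 2.3 points).

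Two stronger readings are tempting and should be resisted:

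- That the rule itself creates a 21% error rate. It does not; the rule only attaches the wrong words to an ordinary type II error.
- That no non-significant result could be informative. Results with a small enough observed gain would rule out the planned benefit, though not every smaller one.

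The figures rest on a 73% control rate, 325 evaluable patients per arm and normal approximations. The sample size section states no loss rate. If usable data fell by an assumed 10% to 20%, the 21% would become about 26% to 31% on a complete-case approximation, whereas SAP 6.5.3 plans multiple imputation. The direction of the point does not depend on these assumptions.

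**What to change.** Keep the stop in step 1a and replace only its conclusion. Suggested wording:

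*Stop; a difference in angiographic occlusion was not demonstrated. Interpret the result using the risk ratio and its 95% CI (section 6.5.1), including whether the CI excludes the design effect (73% vs 82%, risk ratio about 1.12).*

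Leave steps 2a to 4a as they are. The cost is one sentence in the SAP, which allows revisions before data lock. No test, significance level, sample size, estimate or interval changes.
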